8.1.3. Serious Breach of Protocol

Investigators must notify the Medical Monitor within 24 hours of becoming aware of a potential serious breach of the protocol. A serious breach is a breach that is likely to affect to a significant degree the safety and rights of a study participant or the reliability and robustness of the data generated in the clinical trial.

8.1.4. Study Documentation, Confidentiality, and Records Retention

All documentation relating to the study should be retained for 2 years after the last approval in an ICH territory or as locally required, whichever is longer. If it becomes necessary for the Sponsor, the Sponsor's designee, applicable IRB/IEC, or applicable regulatory authorities to review or audit any documentation relating to the study, the Investigator must permit direct access to all source documents/data. Records will not be destroyed without informing the

Sponsor in writing and giving the Sponsor the opportunity to store the records for a longer period of time at the Sponsor's expense.

The Investigator must ensure that the patients' confidentiality will be maintained. On the eCRFs or other documents submitted to the Sponsor or designees, patients should not be identified by their names, but by the assigned patient number or code. If patient names are included on copies of documents submitted to the Sponsor or designees, the names will be obliterated, and the assigned patient number added to the document. Documents not for submission to the Sponsor (eg, signed ICFs) should be maintained by the Investigator in strict confidence.

The Investigator must treat all of the information related to the study and the compiled data as confidential, whose use is for the purpose of conducting the study. The Sponsor must approve any transfer of information not directly involved in the study.

To comply with local and/or regional regulations, this clinical study may be registered, and study results may be posted on public registries, such as ClinicalTrials.gov.

8.1.5. End of Study

The end of study is defined as the last patient last visit.

8.1.6. Termination of the Clinical Study or Site Closure

The Sponsor, or designee, reserves the right to terminate the study or a clinical study site at any time. Conditions that may warrant this action may include, but are not limited to:

- The discovery of an unexpected, serious, or unacceptable risk to patients participating in the study
- Failure of the Investigator to comply with the protocol, the requirements of the IRB/IEC or local health authorities, the sponsor's procedures, or GCP guidelines
- Inadequate recruitment of participants by the Investigator
- The decision on the part of the Sponsor to suspend or discontinue treatment with the study drug

Should the study be terminated, and/or the site closed for whatever reason, all documentation and study drug pertaining to the study must be returned to the Sponsor or its representative, and the Investigators, IRB/IEC and Regulatory Authorities will be promptly informed of the termination and the reason for the decision. The Investigator should promptly inform the patients and assure appropriate therapy and follow-up.

8.2. Data Quality Control and Quality Assurance

8.2.1. Data Handling

Study data must be recorded on CRFs (paper and/or electronic) provided by the Sponsor or designee on behalf of the Sponsor. Case report forms must be completed only by persons designated by the Investigator. If eCRFs are used, study data must be entered by trained site personnel with access to a valid and secure eCRF system. All data entered into the eCRF must also be available in the source documents. Corrections on paper CRFs must be made so as to not

obliterate the original data and must be initialed and dated by the person who made the correction.

8.2.2. Study Monitoring

The Monitor, as a representative of the Sponsor, has an obligation to closely follow the study conduct at the site. The Monitor will visit the Investigator and clinical study center periodically and will maintain frequent telephone and written contact. The Monitor will maintain current personal knowledge of the study through observation, review of study records and source documentation, and discussion of the conduct of the study with the Investigator and staff.

The Monitor will review source documents, systems and CRFs to ensure overall quality and completeness of the data and to confirm study procedures are complied with the requirements in the study protocol accurately. The Sponsor, or its designee, will be allowed to conduct site visits to the investigation facilities for the purpose of monitoring any aspect of the study. The Investigator agrees to allow the Monitor to inspect the drug storage area, study drug stocks, drug accountability records, patient charts and study source documents, site standard operating procedures and training records, and other records relative to study conduct.

8.2.3. Audits and Inspections

Periodically, the Sponsor or its authorized representatives audit clinical investigative sites as an independent review of core trial processes and documents to determine whether these activities were conducted, and data were recorded, analyzed, and accurately reported according to the protocol, GCP guidelines of the ICH, and any applicable regulatory requirements. A regulatory authority, an IEC or an IRB may visit the site to perform audits or inspections, including source data verification. The Investigator should contact the Sponsor and designee immediately if contacted by a regulatory agency, an IEC or an IRB about an inspection.

8.3. Publication Policy

It is intended that after completion of the study, the data are to be submitted for publication in a scientific journal and/or for reporting at a scientific meeting. A copy of any proposed publication (eg, manuscript, abstracts, oral/slide presentations, book chapters) based on this study, must be provided and confirmed received at the Sponsor at least 30 days before its submission. The Clinical Trial Agreement among the institution, Investigator, and Alnylam will detail the procedures for Alnylam's review of publications.

Authorship of any publications resulting from this study will be determined on the basis of the Uniform Requirement for Manuscripts Submitted to Biomedical Journals (International Committee of Medical Journal Editors).

10. APPENDICES

10.1. Formulae for Estimated Glomerular Filtration Rate Calculation

Estimated glomerular filtration rate (eGFR; in mL/min/1.73 m²) will be calculated from serum creatinine (SCr) based on the Schwartz Bedside Formula for patients \geq 12 months to $<$ 18 years of age, and the Modification of Diet in Renal Disease Formula for patients \geq 18 years of age.

Schwartz Bedside Formula [Schwartz 2009]

- Conventional units
 - $eGFR \text{ (mL/min/1.73 m}^2\text{)} = (0.413 \times \text{height [cm]})/\text{SCr (mg/dL)}$
- SI units
 - $eGFR \text{ (mL/min/1.73 m}^2\text{)} = (36.2 \times \text{height [cm]})/\text{SCr (\mu mol/L)}$

Modification of Diet in Renal Disease Formula[Levey 2009]

- Conventional units
 - $eGFR \text{ (mL/min/1.73m}^2\text{)} = 175 \times (\text{SCr [mg/dL]})^{-1.154} \times (\text{age})^{-0.203} \times (0.742, \text{ if female}), \text{ or } \times (1.212, \text{ if African American})$
- SI units
 - $eGFR \text{ (mL/min/1.73m}^2\text{)} = 175 \times (\text{SCr [\mu mol/L]}/88.4)^{-1.154} \times (\text{age})^{-0.203} \times (0.742, \text{ if female}), \text{ or } \times (1.212, \text{ if African American})$

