4.1.1. Cohorts A and B

Age

1. Have reached at least 37 weeks estimated gestational age (full-term infant) at consent (or assent).

Patient and Disease Characteristics

2. Documentation or confirmation of PH1 as determined by genetic analysis prior to initial dosing.
3. Patients with eGFR ≤ 45 mL/min/1.73 m² as calculated by the MDRD formula if ≥ 18 years or Schwartz Bedside Formula if ≥ 12 months to <18 years, or patients <12 months of age with serum creatinine that is considered elevated for age at consent.

4. The mean of the three most recent screening plasma oxalate samples collected prior to Day 1 is $\geq 20 \mu\text{mol/L}$. In Cohort B, these 3 collections may include the first pre-dialysis sample from each plasma oxalate profile.
5. If taking therapeutic vitamin B6 (pyridoxine), must have been on stable regimen for at least 90 days before consent, and is able and willing to remain on this stable regimen until at least the Month 6 visit. Dose adjustments for interval weight gain are acceptable.

Informed Consent

6. Patient is willing and able to comply with the study requirements and to provide written informed consent. In the case of patients under the age of legal consent, the legal guardian(s) must provide informed consent and the patient should provide assent per local and national requirements.

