3.2. Secondary Endpoints

The following are the secondary endpoints in the Primary Analysis Period:

Primary Analysis Period (Baseline to 6 months)

- Percent change in plasma oxalate AUC between dialysis sessions (Cohort B)
- Absolute change in plasma oxalate
- Change in the following parameters:
 - Urinary oxalate, which is measured by percent and absolute change in 24-hour urinary oxalate excretion corrected for BSA and spot urinary oxalate:creatinine ratio, when available.
 - QoL assessed by the PedsQL Total Score for patients ≥ 2 to < 18 years of age at consent, and as assessed by KDQOL Burden of Kidney Disease and Effect of Kidney Disease on Daily Life subscales, and SF-12 Physical Component Summary and Mental Component Summary, in patients ≥ 18 years at consent
- Plasma PK parameters of lumasiran

The following are the secondary endpoints in the Long-term Extension Period:

Long-term Extension Period (6 months to end of study)

- Percent change in plasma oxalate AUC between dialysis sessions (Cohort B)
- Percent and absolute change in plasma oxalate
- Change in the following parameters:
 - Nephrocalcinosis as assessed by renal ultrasound
 - Frequency and mode of dialysis (Cohort B)
 - Frequency of renal stone events
 - Urinary oxalate, measured by 24-hour urinary oxalate excretion corrected for BSA, and spot urinary oxalate:creatinine ratio
 - Renal function as assessed by eGFR (Cohort A)
 - Measures of systemic oxalosis in the following systems:
 - Cardiac

- Dermatologic
- Skeletal
- Ocular
- QoL (quality of life) assessed by the PedsQL Total Score for patients ≥ 2 to < 18 years of age at consent, and as assessed by KDQOL Burden of Kidney Disease and Effect of Kidney Disease on Daily Life subscales, and SF-12 Physical Component Summary and Mental Component Summary, in patients ≥ 18 years at consent

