7.6.3. Clinical Laboratory Data

Clinical laboratory parameters will be expressed in Standard International (SI) units. Laboratory data collected and recorded as below the lower limit of detection (LLOD) will be set to the LLOD for calculation of summary statistics. Summaries will only include data from central laboratory. For any local collections of LFTs, these will be included in a separate data listing. Key laboratory parameters will be graded according to NCI CTCAE v5.0 or later.

Summaries for each lab parameter (hematology, chemistry, liver function tests, and urinalysis) that are continuous variables, will have a tabular summary of descriptive statistics at each scheduled visit. Descriptive statistics include actual value, change from baseline and percent change from baseline at each scheduled visit.

Shift tables will be generated to summarize shifts from baseline category to the worst post-baseline category with directionality specified (eg hyper and hypo), including eGFR when applicable.

Clinical laboratory tests with normal ranges will be classified as Low, Normal, and High. For these tests, abnormal values will be flagged in the listings with H when the value is higher than

the upper limit of the reference ranges and with L when the value is lower than the lower limit of the reference ranges.

For hematology and chemistry labs, summary tables of potentially clinically significant abnormalities may also be provided.

All laboratory data will be presented in data listings. Separate listings will be included for those laboratory data collected from local labs such as LFTs. Out of range laboratory results will be identified in listings.

LFTs: A listing will be generated for all patients with abnormal liver function tests as defined by alanine aminotransferase (ALT)>3xULN, aspartate aminotransferase (AST)>3xULN or total bilirubin >2x ULN at any visit, where age specific ULN (when applicable) may be used.

A tabular summary for LFTs will be generated to summarize the number and associated percentage of patients in each of the categories at any post-baseline visit:

- Within normal limit (WNL), $1 < \text{ALT} \leq 3$, $3 < \text{ALT} \leq 5$, $5 < \text{ALT} \leq 10$, $10 < \text{ALT} \leq 20$, $\text{ALT} > 20 \times \text{ULN}$
- WNL, $1 < \text{AST} \leq 3$, $3 < \text{AST} \leq 5$, $5 < \text{AST} \leq 10$, $10 < \text{AST} \leq 20$, $\text{AST} > 20 \times \text{ULN}$

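### Protocol Appendix 10.1: the two Schwartz constants do not convert into each other, and the MDRD factors joined by *or* give no single eGFR for an adult who is both female and African American

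*Protocol*

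**What the plan says.** Appendix 10.1 of the protocol presents each eGFR formula in conventional and SI units as equivalent forms. For the Schwartz formula the conventional line is "0.413 \times \text{height [cm]})/\text{SCr (mg/dL" and the SI line uses "36.2 \times \text{height [cm" over creatinine in µmol/L. The SI line of the MDRD formula, in the same appendix, divides creatinine by 88.4. Both MDRD lines end with the two adjustment factors written as "0.742, \text{ if female}), \text{ or } \times (1.212, \text{ if African American".

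Inclusion criterion 3 (Protocol 4.1.1) requires eGFR ≤45 mL/min/1.73 m² "as calculated by the MDRD formula if ≥ 18 years or Schwartz Bedside Formula" for ages 12 months to under 18 years. Patients under 12 months enter on serum creatinine elevated for age and do not use either formula. Protocol 6.3.4 collects eGFR as an assessment only in patients not on dialysis. The SAP (3.2) lists "Renal function as assessed by eGFR (Cohort A") among the secondary endpoints of the Long-term Extension Period. SAP 6.2, 7.2 and 7.6.3 also use eGFR as a baseline characteristic, a possible Cohort A subgroup and a shift-table parameter. The SAP gives no eGFR formula of its own.

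**The concern.** Two forms of one formula should give the same answer for the same patient, and a formula should give one answer for every patient it covers. Appendix 10.1 fails the first test for Schwartz and the second for MDRD. What is at stake is the reproducibility of an eligibility decision for patients near the cut-off, and of absolute eGFR values in Cohort A during the extension. Planned enrolment is 20, so one patient classified differently is 1/20 = 5% of the study.

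The two defects have different causes and sizes and should be read separately. The Schwartz mismatch could touch any child aged 12 months or more, but it is small. The MDRD ambiguity touches only adults who are both female and African American, but for them it is large.

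**Working it through.** **Inputs.** From Appendix 10.1: Schwartz constants 0.413 (mg/dL) and 36.2 (µmol/L); creatinine conversion 88.4; MDRD equation 175 × SCr^−1.154 × age^−0.203; factors 0.742 and 1.212. From Protocol 4.1.1: cut-off 45.

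**1. Schwartz pair.** The SI constant should equal the conventional constant × 88.4.

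- 0.413 × 88.4 = 36.51; the appendix states 36.2, so its figure is not reproduced.
- Rounding of 0.413 does not explain it: 0.4125 × 88.4 = 36.47 and 0.4135 × 88.4 = 36.55.
- Working back, 36.2 / 88.4 = 0.4095. A constant of 0.41 gives 0.41 × 88.4 = 36.24, which rounds to 36.2.
- Ratio of SI to conventional result: 36.2 / 36.51 = 0.9915, so the SI line is 0.85% lower.
- At the cut-off, an SI value of 45.00 corresponds to 45.00 / 0.9915 = 45.38 conventional, and 45.00 conventional corresponds to 44.62 SI. The difference is about 0.4 mL/min/1.73 m².
- Example: height 150 cm, creatinine 1.37 mg/dL (1.37 × 88.4 = 121.1 µmol/L). Conventional: 0.413 × 150 / 1.37 = 45.22, not eligible. SI: 36.2 × 150 / 121.1 = 44.84, eligible.

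If the same line is used at baseline and follow-up, the constant k cancels in percent change: (k·x₁ − k·x₀)/(k·x₀) = (x₁ − x₀)/x₀. Absolute change shifts by 0.85%.

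**2. MDRD factors.** The conventional and SI lines agree exactly, because the SI line only divides by 88.4. The question is which factor applies to an adult who meets both conditions.

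- Female factor only: 0.742.
- African American factor only: 1.212.
- Both: 0.742 × 1.212 = 0.899.
- Largest spread: 1.212 / 0.742 = 1.63-fold.

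Examples at age 30:

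| SCr (mg/dL) | Unadjusted | × 0.742 | × 1.212 | × 0.899 |
|---|---|---|---|---|
| 1.6 | 51.0 | 37.9 | 61.8 | 45.9 |
| 2.0 | 39.4 | 29.3 | 47.8 | 35.5 |
| 2.5 | 30.5 | 22.6 | 36.9 | 27.4 |

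The unadjusted value at which each reading meets ≤45 is 45 / 0.742 = 60.6, 45 / 0.899 = 50.0 and 45 / 1.212 = 37.1. So for such a patient:

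- at or below about 37.1 unadjusted, every reading makes her eligible;
- above about 37.1 and up to 60.6, at least two readings disagree;
- above about 50.0 and up to 60.6, the two readings that apply the female factor disagree with each other.

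As with Schwartz, a factor applied consistently cancels in one patient's percent change; absolute values and absolute change scale with it.

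**The case against.** The strongest objection is about weight. The Schwartz gap is about 0.4 mL/min/1.73 m² at the cut-off and matters only in a band from just above 45.00 to 45.38. Planned enrolment names 4 patients under 6 years and 2 aged 6 to under 18 (Protocol 7.1; SAP 5.1 makes these minimums), and infants under 12 months do not use the formula. For MDRD, each factor carries its own condition and its own multiplication sign, so applying each when its condition holds is a natural reading. The examples that cross the cut-off lie near it, and the documents give no count of affected patients. All of this stands, and it is why the point is minor. It does not give the appendix a consistent Schwartz pair or a written rule for the MDRD factors.

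A reader might infer two stronger things. The first is that the SI line is known to be the one in use, because SAP 7.6.3 says "Clinical laboratory parameters will be expressed in Standard International (SI) units". That sentence governs how laboratory results are presented. It does not say which line of Appendix 10.1 the laboratory programs or which line screening uses. Protocol 6.5.5 makes central testing the rule, with local testing where blood volume limits prevent it, and SAP 7.6.3 restricts summaries to central data. If one line is used throughout, no mixing of units reaches the analysis.

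The second is that 36.2 is the wrong number and 0.413 the right one. The documents show only that the two disagree. 36.2 fits a constant of 0.41, and the cited source for the formula is not part of the documents.

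**Conclusion.** Both defects are real, and nothing else in the protocol or SAP resolves them. The Schwartz pair is inconsistent by 0.85%. This changes eligibility only for a child with conventional eGFR above 45.00 and up to 45.38, and has no effect on percent change if one line is used throughout. The MDRD wording leaves adults who are both female and African American with a factor of 0.742, 1.212 or 0.899, which can change eligibility when the unadjusted value is above about 37.1 and up to 60.6.

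The consequences are limited to inclusion criterion 3, the Cohort A eGFR endpoint in the long-term extension, and descriptive uses of eGFR. The primary endpoint is plasma oxalate, so the primary analysis is touched only through who is enrolled. The arithmetic rests on 88.4 as the conversion factor, which the appendix itself uses. How many patients are affected, and which formula line is in operation, cannot be determined from the documents. This is a low-severity correction that is worth making because it costs almost nothing.

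**What to change.** In Appendix 10.1:

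- Check the Schwartz constants against the cited source and make the pair consistent at 88.4. If 0.413 is confirmed as governing, the SI constant becomes 36.5; if not, correct the conventional constant (36.2 corresponds to 0.4095).
- State which unit line is used for eligibility and for analysis, and use it throughout.
- Write the MDRD factors as separate multipliers, × 0.742 if female and × 1.212 if African American, each applied when its condition holds.

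Repeat or cross-reference the final formulas in the SAP, which currently has none. Confirm what the central laboratory has programmed. If it differs from the corrected text, recheck eligibility for any enrolled child whose value lies between the two Schwartz lines at the cut-off, and for any adult to whom both MDRD factors apply. The cost is two short appendix edits, a sentence in the SAP and one query to the laboratory.

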10.2. Blood Volume Limits in Pediatric Patients

The maximum blood volume, which will be collected from pediatric patients over the course of the study, will be based on age and weight and will not exceed those specified in Table 15, which was adapted from the Feinstein Institute for Medical Research Human Subject Protection Program Guidance Document.

Table 15: Maximum Allowable Total Blood Volume Collection Chart

Body Weight (kg)	Body Weight (lbs)	Total Blood Volume (mL)	Maximum Allowable Volume in a 24-hour Period		Total Volume Collected in a 30-day Period	
			2.5% of total blood volume (mL)	3% of total blood volume (mL)	5% of total blood volume (mL)	10% of total blood volume (mL)
1	2.2	100	2.5	3	5	10
2	4.4	200	5	6	10	20
3	6.6	240	6	7.2	12	24
4	8.8	320	8	9.6	16	32
5	11	400	10	12	20	40
6	13.2	480	12	14.4	24	48
7	15.4	560	14	16.8	28	56
8	17.6	640	16	19.2	32	64
9	19.8	720	18	21.6	36	72
10	22	800	20	24	40	80
11-15	24-33	880-1200	22-30	26.4-36	44-60	88-120
16-20	35-44	1280-1600	32-40	38.4-48	64-80	128-160
21-25	46-55	1680-2000	42-50	50.4-60	84-100	168-200
26-30	57-66	2080-2400	52-60	62.4-72	104-120	208-240
31-35	68-77	2480-2800	62-70	74.4-84	124-140	248-280
36-40	79-88	2880-3200	72-80	86.4-96	144-160	288-320
41-45	90-99	3280-3600	82-90	98.4-108	164-180	328-360
46-50	101-110	3680-4000	92-100	110.4-120	184-200	368-400
51-55	112-121	4080-4400	102-110	122.4-132	204-220	408-440
56-60	123-132	4480-4800	112-120	134.4-144	224-240	448-480
61-65	134-143	4880-5200	122-130	146.4-156	244-260	488-520
66-70	145-154	5280-5600	132-140	158.4-168	264-280	528-560
71-75	156-165	5680-6000	142-150	170.4-180	284-300	568-600
76-80	167-176	6080-6400	152-160	182.4-192	304-360	608-640
81-85	178-187	6480-6800	162-170	194.4-204	324-340	648-680
86-90	189-198	6880-7200	172-180	206.4-216	344-360	688-720
91-95	200-209	7280-7600	182-190	218.4-228	364-380	728-760
96-100	211-220	7680-8000	192-200	230.4-240	384-400	768-800

Adapted from <http://www.feinsteininstitute.org/wp-content/uploads/2013/02/Maximum-Blood-Draw-Limits.pdf>. [Feinstein_Institute 2013]

**ALN-GO1-005 PROTOCOL AMENDMENT 1
SUMMARY OF CHANGES DATED 06 MAY 2020**

ILLUMINATE-C: A Single Arm Study to Evaluate Efficacy, Safety, Pharmacokinetics, and Pharmacodynamics of Lumasiran in Patients with Advanced Primary Hyperoxaluria Type 1 (PH1)

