6.5.5.4. Maximum Blood Volume

The maximum blood volume, which will be collected from pediatric patients over the course of the study, will be based on age and weight and will not exceed those specified in Table 15 from the Feinstein Institute for Medical Research Human Subject Protection Program Guidance Document (see Appendix Section 10.2). [Feinstein_Institute 2013] Consult the Laboratory Manual for the blood draw priority list based on patient weight.

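### One limit in the paediatric blood-volume table is wrong: the 5% cap for 76-80 kg is printed as 304-360 mL and should be 304-320 mL

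*Protocol*

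**What the plan says.** Protocol Section 6.5.5.4 sets the rule. "The maximum blood volume, which will be collected from pediatric patients over the course of the study" depends on age and weight and "will not exceed those specified in Table 15 from the Feinstein Institute" guidance document. Appendix Section 10.2 repeats that volumes "will be based on age and weight and will not exceed those specified in Table 15" and then gives the table, which is described as adapted from that outside source.

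Table 15 has 28 weight rows from 1 kg to 96-100 kg. Each row states a total blood volume and four limits: 2.5% and 3% of that volume for a 24-hour period, and 5% and 10% for a 30-day period. There is no age column, and no note says which percentage applies to which patient.

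The 76-80 kg row reads: total blood volume 6080-6400 mL; 24-hour limits 152-160 and 182.4-192 mL; 30-day limits 304-360 mL (5%) and 608-640 mL (10%).

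Section 6.5.5.4 also refers sites elsewhere, but for a different purpose: "Consult the Laboratory Manual for the blood draw priority list based on patient weight".

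**The concern.** The 5% entry in the 76-80 kg row does not agree with the blood volume in the same row. It also breaks the sequence of the column, because the cap for an 80 kg patient is higher than the cap for an 85 kg patient. The protocol makes the table an operating limit, so a wrong cell is a wrong limit and not just a slip in background text. A site that follows the table could draw more than the column's own percentage allows and still be compliant.

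A smaller question sits beside it. The text promises limits by age and weight, but the table is indexed by weight alone and gives two figures for each period. A reader has to infer which one governs.

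**Working it through.** **Inputs**, all from Table 15 in Protocol Section 10.2: the stated total blood volume in each row, and the four column percentages (2.5%, 3%, 5%, 10%).

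**Formula.** Limit (mL) = column percentage × stated total blood volume (mL), taken at the single value, or at both ends of the range, in each row.

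**Number of values.** Ten rows (1 to 10 kg) carry a single value and 18 rows carry a range: 10 × 4 + 18 × 2 × 4 = 40 + 144 = 184.

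**Blood volume against weight.** The stated volumes equal 100 mL/kg at 1 and 2 kg and 80 mL/kg in every other row. At 80 kg this gives 80 × 80 = 6400 mL, so the blood volume in the row at issue is correct.

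**The row at issue**

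| Column | Computed from 6080-6400 mL | Printed | Agrees |
|---|---|---|---|
| 2.5%, 24 hours | 152-160 | 152-160 | yes |
| 3%, 24 hours | 182.4-192 | 182.4-192 | yes |
| 5%, 30 days | 304-320 | 304-360 | lower end only |
| 10%, 30 days | 608-640 | 608-640 | yes |

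**Whole table.** 183 of the 184 values reproduce exactly. The upper end of the 5% cell in this row is the only mismatch.

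**Size of the error**
- 360 − 320 = 40 mL.
- 40 / 320 = 12.5% above the column's own limit.
- 360 / 6400 = 5.625% of blood volume, against the stated 5%.

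**Neighbouring rows, 5% column**
- 71-75 kg: 284-300.
- 76-80 kg: 304-360 printed, 304-320 computed.
- 81-85 kg: 324-340.
- 86-90 kg: 344-360.

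Upper ends of 300, 320, 340 and 360 rise by 20 mL per row. As printed, the 80 kg cap exceeds the 85 kg cap by 360 − 340 = 20 mL. It equals the correct cap for 90 kg (0.05 × 7200 = 360).

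**Two columns per period.** The higher limit is 3 / 2.5 = 1.2 times the lower for 24 hours and 10 / 5 = 2 times the lower for 30 days, at every weight. For a 4 kg infant (320 mL) the figures are 8 or 9.6 mL per 24 hours and 16 or 32 mL per 30 days. If volumes must not exceed any figure specified for the patient's weight, the lower figure in each pair governs: 2.5% and 5%. On that reading the wrong cell lies in a column that binds.

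**The case against.** The strongest reply is that nothing practical follows from the cell. It concerns the top of one weight band in a table for children. Planned paediatric enrolment is 4 patients under 6 years and 2 aged 6 to under 18 (Protocol Sections 3.4 and 7.1; the SAP, Section 5.1, says at least that many), and few if any are likely to weigh about 80 kg. The printed 360 mL is well under the 640 mL in the same row's 10% column. The neighbouring rows make the slip easy to see, and it may have come from the source document. All of this stands as to consequence. It does not make the number right, and the protocol gives the table binding force.

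A reader might infer something stronger from the paired columns: that the protocol contradicts itself, or that sites will apply caps differing twofold to the same infant and so draw too much. The documents do not support that.
- Not exceeding the specified volumes can be read as satisfying both columns, so a conservative reading is available. The gap is one of clarity.
- No per-sample volumes are given, so no scheduled draw can be shown to approach either limit.
- The plan already adapts sampling to blood volume. The oxalate profile is up to 8 samples, subject to volume limits (Section 6.2.1.2). Very young patients may have panels run locally (Section 6.5.5). The hepatic work-up may be staggered (Section 6.5.5.3 and Table 14). Extra PK samples are taken only where volume allows (Tables 5 and 6). The SAP expects some blood results to be missing for this reason (Section 5.5).
- Profile and PK sampling do not coincide routinely. In the primary analysis period the two schedules meet only at Month 6 (Tables 1 and 6).

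The Laboratory Manual may say which column applies. It is not among the documents, so this cannot be excluded. The protocol cites it for draw priority and not for a volume limit.

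**Conclusion.** The 5% limit at the upper end of the 76-80 kg row is wrong: 360 mL is printed where the table's own inputs give 320 mL, an excess of 40 mL or 12.5%. The conclusion needs no outside figure. It assumes only that the column heading and the stated blood volume are as intended, and the row's other three columns and the adjacent rows support both.

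The practical effect is small, since only a paediatric patient near 80 kg is touched. That few such patients will enrol is an assumption, because the protocol gives no expected weights.

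The missing statement of which column binds is a secondary clarification. It shows neither a contradiction nor an unsafe draw, but it is worth settling because the text names age as a determinant and the table does not use it.

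Severity is minor. The primary endpoint and its analysis are unaffected, and so is the sample size, which was set on feasibility.

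**What to change.** In Table 15, change the 5% entry for 76-80 kg from 304-360 to 304-320, after confirming the cell against the typeset page.

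In the same edit, add one sentence to Sections 6.5.5.4 and 10.2 naming the column that binds for the 24-hour and for the 30-day period. If the lower columns are meant (2.5% and 5%), say so. If the higher ones are meant for some patients, state the age, weight or health criterion. If age plays no part, delete the reference to it. The choice of limit is for the sponsor's medical reviewers. The Laboratory Manual should be checked so that it agrees.

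The cost is one corrected cell and one added sentence in each section. No patient, visit, sample or analysis changes.
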